6.7 Recommended Dose Modifications for Nivolumab (OPDIVO™)

Table 1: Adverse Reaction	Severity	Dose Modification
Colitis	Grade 2 diarrhea or colitis	Withhold dose ^a
	Grade 3 diarrhea or colitis	
	Single-agent OPDIVO	Withhold dose ^a
	OPDIVO, in combination with ipilimumab	Permanently discontinue
	Grade 4 diarrhea or colitis	Permanently discontinue
Pneumonitis	Grade 2 pneumonitis	Withhold dose ^a
	Grade 3 or 4 pneumonitis	Permanently discontinue
Hepatitis	Aspartate aminotransferase (AST)/or alanine aminotransferase (ALT) more than 3 and up to 5 times the upper limit of normal or total bilirubin more than 1.5 and up to 3 times the upper limit of normal	Withhold dose ^a
	AST or ALT more than 5 times the upper limit of normal or total bilirubin more than 3 times the upper limit of normal	Permanently discontinue
Hypophysitis	Grade 2 or 3 hypophysitis	Withhold dose ^a
	Grade 4 hypophysitis	Permanently discontinue
Adrenal Insufficiency	Grade 2 adrenal insufficiency	Withhold dose ^a
	Grade 3 or 4 adrenal insufficiency	Permanently discontinue
Nephritis and Renal Dysfunction	Serum creatinine more than 1.5 and up to 6 times the upper limit of normal	Withhold dose ^a
	Serum creatinine more than 6 times the upper limit of normal	Permanently discontinue
Rash	Grade 3 rash	Withhold dose ^a
	Grade 4 rash	Permanently discontinue
Encephalitis	New onset moderate or severe neurologic signs or symptoms	Withhold dose ^a
	Immune-mediated encephalitis	Permanently discontinue
Other	Other Grade 3 adverse reaction	
	First occurrence	Withhold dose ^a
	Recurrence of same Grade 3 adverse reactions	Permanently discontinue
	Life-threatening or Grade 4 adverse reaction	Permanently discontinue
	Requirement for 10 mg per day or greater prednisone or equivalent for more than 12 weeks	Permanently discontinue
	Persistent Grade 2 or 3 adverse reactions lasting 12 weeks or longer	Permanently discontinue

^a Resume Treatment when adverse reaction returns to Grade 0 or 1

6.8 Recommended Dose Modification for Pembrolizumab (Keytruda)

Withhold KEYTRUDA for any of the following:

Grade 2 pneumonitis [see *Warnings and Precautions (5.1) of FDA insert*]

Grade 2 or 3 colitis [see *Warnings and Precautions (5.2) of FDA insert*]

Grade 3 or 4 endocrinopathies [see *Warnings and Precautions (5.4) of FDA insert*]

Grade 2 nephritis [see *Warnings and Precautions (5.5) of FDA insert*]

Aspartate aminotransferase (AST) or alanine aminotransferase (ALT) greater than 3 and up to 5 times upper limit of normal (ULN) or total bilirubin greater than 1.5 and up to 3 times ULN

Any other severe or Grade 3 treatment-related adverse reaction [see *Warnings and Precautions (5.6) of FDA insert*]

Resume KEYTRUDA in patients whose adverse reactions recover to Grade 0-1.

Permanently discontinue KEYTRUDA for any of the following:

Any life-threatening adverse reaction (excluding endocrinopathies controlled with hormone replacement therapy)

Grade 3 or 4 pneumonitis or recurrent pneumonitis of Grade 2 severity [see *Warnings and Precautions (5.1) of FDA insert*]

Grade 3 or 4 nephritis [see *Warnings and Precautions (5.5) of FDA insert*]

AST or ALT greater than 5 times ULN or total bilirubin greater than 3 times ULN

For patients with liver metastasis who begin treatment with Grade 2 AST or ALT, if AST or ALT increases by greater than or equal to 50% relative to baseline and lasts for at least 1 week

Grade 3 or 4 infusion-related reactions [see *Warnings and Precautions (5.7) of FDA insert*]

Inability to reduce corticosteroid dose to 10 mg or less of prednisone or equivalent per day within 12 weeks

Persistent Grade 2 or 3 adverse reactions (excluding endocrinopathies controlled with hormone replacement therapy) that do not recover to Grade 0-1 within 12 weeks after last dose of KEYTRUDA

Any severe or Grade 3 treatment-related adverse reaction that recurs [see *Warnings and Precautions (5.6) of FDA insert*]

7.0 Measurement of Effect

7.1 Assessment for efficacy

The following efficacy parameters will be assessed by the investigator and are defined as follows:

Objective response rate: the proportion of subjects who achieve complete or partial response according to the investigator's assessment. RECIST measurements should be performed by the investigator as the gold-standard for classifying response.

Duration of best response: the duration of time from the date of response until the first date of progression as determined by the investigator or death, whichever comes first

Disease control rate: the percentage of subjects who achieved CR, PR, or SD which is sustained for at least 3 months.

Duration of disease control: the duration of time from the date of first response until the first date of progression or death, whichever comes first

7.2 Survival Outcomes

Progression-Free Survival is defined as the duration of time from the start of treatment to the time of investigator assessed progression, death, or date of last contact.

Overall Survival is defined as the duration of time from the date of progression on current treatment targeting the primary oncogenic driver to date of death or date of last contact.

8.0 Adverse Events List and Reporting Requirements

8.1 Adverse Event list for Pembrolizumab

Most common adverse reactions (reported in $\geq 20\%$ of patients) with:

- NSCLC included fatigue, decreased appetite, dyspnea and cough.

Adverse Reactions in $\geq 10\%$ of Patients with NSCLC Pembrolizumab 2 mg/kg every 3 weeks or 10 mg/kg every 2 or 3 weeks N=550		
Adverse Reaction	All Grades (%)	Grade 3* (%)
General Disorders and Administration Site Conditions		
Fatigue†	44	4
Pyrexia	12	1
Peripheral Edema	10	0
Metabolism and Nutrition Disorders		

Phase II Pilot Study Evaluating Strategies to Overcome Resistance at the Time of Progression
 for Patients with Non-Small Cell Lung Cancers Harboring Major Oncogenic Drivers
 Wake Forest Baptist Comprehensive Cancer Center (CCCFWU)
 CCCFWU 62716
 ClinicalTrials.gov: NCT02949843

Decreased appetite	25	1
Respiratory, Thoracic and Mediastinal Disorders		
Dyspnea	23	4
Cough [†]	29	<1
Gastrointestinal Disorders		
Nausea	18	1
Diarrhea	15	1
Constipation	15	<1
Vomiting	12	1
Musculoskeletal and Connective Tissue Disorders		
Arthralgia	15	1
Back pain	10	2
Blood and Lymphatic System Disorders		
Anemia	12	2
Skin and Subcutaneous Tissue Disorders		
Pruritus	12	0
Rash [§]	18	<1

* Of the $\geq 10\%$ adverse reactions, none was reported as Grade 4 or 5.

[†] Includes the terms fatigue and asthenia

[‡] Includes the terms cough, productive cough and hemoptysis

[§] Includes the terms dermatitis, dermatitis acneiform, erythema multiforme, drug eruption, rash, rash generalized, rash pruritic, rash macular/maculopapular, papular

8.2 Adverse Event List for Nivolumab

Most common adverse reactions have included fatigue, cough, nausea, pruritus, rash, decreased appetite, constipation, arthralgia, thyroid function abnormalities, and diarrhea. The most frequent serious adverse drug reactions were renal failure, dyspnea, and pneumonitis. Additional AEs are listed below:

Adverse Effects

>10% (All grades)

NSCLC

- Fatigue (50%)
- Lymphopenia (47%)
- Dyspnea, hyponatremia (38%)
- Musculoskeletal pain (36%)
- Cough (32%)
- Nausea (29%), anemia (28%), constipation (24%)
- Increases creatinine (22%)
- Hypercalcemia, hypokalemia, hypomagnesemia (20%)
- Vomiting, asthenia (19%)
- Hypocalcemia, hyperkalemia, diarrhea (18%)

Phase II Pilot Study Evaluating Strategies to Overcome Resistance at the Time of Progression
for Patients with Non-Small Cell Lung Cancers Harboring Major Oncogenic Drivers
Wake Forest Baptist Comprehensive Cancer Center (CCCFWU)
CCCFWU 62716
ClinicalTrials.gov: NCT02949843

- Edema, pyrexia (17%)
- Abdominal pain, rash, increased AST (16%)
- Increased alkaline phosphatase, thrombocytopenia (14%)
- Chest pain, arthralgia, decreased appetite and weight (13%)
- Increased ALT (12%), pruritus (11%)

1-10% (all grades)

NSCLC

- Pneumonia (10%)
- Pain (10%)

1-10% (grades 3-4)

NSCLC

- Dyspnea (9%)
- Fatigue (7%)
- Musculoskeletal pain (6%)
- Pneumonia (5%)
- Decreased appetite (2.6%)
- Pain (2.6%)
- Nausea (1.7%)
- Abdominal pain (1.7%)
- Asthenia (1.7%)
- Edema (1.7%)
- Cough (1.7%)

1-10% (other clinically important adverse effects)

NSCLC

- General disorders and administration site conditions: Stomatitis
- Nervous system disorders: Peripheral neuropathy
- Infections and infestations: Bronchitis, upper respiratory tract infection

8.3 Adverse Event Characteristics

- **CTCAE term (AE description) and grade:** The descriptions and grading scales found in the revised NCI Common Terminology Criteria for Adverse Events (CTCAE) version 4.0 will be utilized for AE reporting. All appropriate treatment areas should have access to a copy of the CTCAE version 4.0. A copy of the CTCAE version 4.0 can be downloaded from the CTEP web site (<http://ctep.cancer.gov>).
- **'Expectedness':** AEs can be 'Unexpected' or 'Expected' (see Section 7.1 above) for expedited reporting purposes only.

- **Attribution of the AE:**

- Definite – The AE is **clearly related** to the study treatment.
- Probable – The AE is **likely related** to the study treatment.
- Possible – The AE **may be related** to the study treatment.
- Unlikely – The AE is **doubtfully related** to the study treatment.
- Unrelated – The AE is **clearly NOT related** to the study treatment.

8.4 STRC SAE Reporting Requirements

The Safety and Toxicity Reporting Committee (STRC) is responsible for reviewing SAEs for WFBCCC Institutional studies as outlined in Appendix B. STRC currently requires that all unexpected 4 and all grade 5 SAEs on these trials be reported to them for review. All WFBCCC Clinical Research Management (CRM) staff members assisting a Principal Investigator in investigating, documenting and reporting an SAE qualifying for STRC reporting are responsible for informing a clinical member of the STRC as well as the entire committee via the email notification procedure of the occurrence of an SAE.

8.5 WFUHS IRB AE Reporting Requirements

Any unanticipated problems involving risks to subjects or others and adverse events shall be promptly reported to the IRB, according to institutional policy. Reporting to the IRB is required regardless of the funding source, study sponsor, or whether the event involves an investigational or marketed drug, biologic or device. Reportable events are not limited to physical injury, but include psychological, economic and social harm. Reportable events may arise as a result of drugs, biological agents, devices, procedures or other interventions, or as a result of questionnaires, surveys, observations or other interactions with research subjects.

All members of the research team are responsible for the appropriate reporting to the IRB and other applicable parties of unanticipated problems involving risk to subjects or others. The Principal Investigator, however, is ultimately responsible for ensuring the prompt reporting of unanticipated problems involving risk to subjects or others to the IRB. The Principal Investigator is also responsible for ensuring that all reported unanticipated risks to subjects and others which they receive are reviewed to determine whether the report represents a change in the risks and/or benefits to study participants, and whether any changes in the informed consent, protocol or other study-related documents are required.

Any unanticipated problems involving risks to subjects or others occurring at a site where the study has been approved by the WFUHS IRB (internal events) must be reported to the WFUHS IRB within 7 calendar days of the investigator or other members of the study team becoming aware of the event.

Any unanticipated problems involving risks to subjects or others occurring at another site conducting the same study that has been approved by the WFUHS IRB (external events) must be reported to the WFUHS IRB within 7 calendar days of the investigator or other members of the study team becoming aware of the event.

Phase II Pilot Study Evaluating Strategies to Overcome Resistance at the Time of Progression
for Patients with Non-Small Cell Lung Cancers Harboring Major Oncogenic Drivers
Wake Forest Baptist Comprehensive Cancer Center (CCCFWU)
CCCFWU 62716
ClinicalTrials.gov: NCT02949843

Any event, incident, experience, or outcome that alters the risk versus potential benefit of the research and as a result warrants a substantive change in the research protocol or informed consent process/document in order to insure the safety, rights or welfare of research subjects.

9.0 Pharmaceutical Information

A list of the adverse events and potential risks associated with the investigational or commercial agents administered in this study can be found in Section 9.2 for the drugs listed here.

For experimental or targeted drugs directed at secondary mutations, please refer to the FDA or Company package insert for Pharmaceutical information related to adverse events, preparation, administration, storage, stability and disposal.

9.1 Pharmaceutical Accountability

Drug accountability logs will be maintained for agents used under this protocol. These logs shall record quantities of study drug received and quantities dispensed to patients, including lot number, date dispensed, patient identifier number, patient initials, protocol number, dose, quantity returned, balance remaining, and the initials of the person dispensing the medication.

9.2 Pembrolizumab(Keytruda)

Product description:

Pembrolizumab for injection: 50 mg lyophilized powder in single-use vial for reconstitution (3). Pembrolizumab for injection: 100 mg/4 mL (25 mg/mL) solution in a single-use vial. The solution should be clear to slightly opalescent, colorless to slightly yellow. Discard the vial if visible particles are observed

Solution preparation:

Reconstitution of KEYTRUDA for Injection (Lyophilized Powder)

- Add 2.3 mL of Sterile Water for Injection, USP by injecting the water along the walls of the vial and not directly on the lyophilized powder (resulting concentration 25 mg/mL).
- Slowly swirl the vial. Allow up to 5 minutes for the bubbles to clear. Do not shake the vial.

Preparation for Intravenous Infusion

- Visually inspect the solution for particulate matter and discoloration prior to administration. The solution is clear to slightly opalescent, colorless to slightly yellow. Discard the vial if visible particles are observed.

Phase II Pilot Study Evaluating Strategies to Overcome Resistance at the Time of Progression
for Patients with Non-Small Cell Lung Cancers Harboring Major Oncogenic Drivers
Wake Forest Baptist Comprehensive Cancer Center (CCCFWU)
CCCFWU 62716
ClinicalTrials.gov: NCT02949843

- Dilute KEYTRUDA injection (solution) or reconstituted lyophilized powder prior to intravenous administration.
- Withdraw the required volume from the vial(s) of KEYTRUDA and transfer into an intravenous (IV) bag containing 0.9% Sodium Chloride Injection, USP or 5% Dextrose Injection, USP. Mix diluted solution by gentle inversion. The final concentration of the diluted solution should be between 1 mg/mL to 10 mg/mL.
- Discard any unused portion left in the vial

Storage requirements: The product does not contain a preservative. Store the reconstituted and diluted solution from the KEYTRUDA 50 mg vial either:

- At room temperature for no more than 6 hours from the time of reconstitution. This includes room temperature storage of reconstituted vials, storage of the infusion solution in the IV bag, and the duration of infusion.
- Under refrigeration at 2°C to 8°C (36°F to 46°F) for no more than 24 hours from the time of reconstitution. If refrigerated, allow the diluted solution to come to room temperature prior to administration.
- Do not freeze

Store the diluted solution from the KEYTRUDA 100 mg/4 mL vial either:

- At room temperature for no more than 6 hours from the time of dilution. This includes room temperature storage of the infusion solution in the IV bag, and the duration of infusion.
- Under refrigeration at 2°C to 8°C (36°F to 46°F) for no more than 24 hours from the time of dilution. If refrigerated, allow the diluted solution to come to room temperature prior to administration.
- Do not freeze.

Stability: Keytruda is stable for no longer than 6 hours at room temperature from the time of reconstitution and no longer than 24 hours under refrigeration at 2°C to 8°C (36°F to 46°F)

9.3 Nivolumab (OPDIVO)

Product description:

OPDIVO is a clear to opalescent, colorless to pale-yellow solution. Discard the vial if the solution is cloudy, discolored, or contains extraneous particulate matter other than a few translucent-to-white, proteinaceous particles.

Phase II Pilot Study Evaluating Strategies to Overcome Resistance at the Time of Progression
for Patients with Non-Small Cell Lung Cancers Harboring Major Oncogenic Drivers
Wake Forest Baptist Comprehensive Cancer Center (CCCFWU)
CCCFWU 62716
ClinicalTrials.gov: NCT02949843

OPDIVO for injection is supplied at 40 mg/4 mL and 100 mg/10 mL in a single use vial.

Solution preparation:

- Withdraw the required volume of OPDIVO and transfer into an intravenous container.
- Dilute OPDIVO with either 0.9% Sodium Chloride Injection, USP or 5% Dextrose Injection, USP to prepare an infusion with a final concentration ranging from 1 mg/mL to 10 mg/mL.
- Mix diluted solution by gentle inversion.
- Do not shake.
- Discard partially used vials or empty vials of OPDIVO

Storage requirements:

The product does not contain a preservative.

After preparation, store the OPDIVO infusion either:

- at room temperature for no more than 4 hours from the time of preparation. This includes room temperature storage of the infusion in the IV container and time for administration of the infusion or
- under refrigeration at 2°C to 8°C (36°F to 46°F) for no more than 24 hours from the time of infusion preparation.
- Do not freeze.

Stability:

OPDIVO is stable for no more than 4 hours at room temperature from the time of preparation and for no more than 24 hours under refrigeration 2°C-8°C (36°F to 46°F)

Route of administration:

Intravenous

Administration

- Administer the infusion over 60 minutes through an intravenous line containing a sterile, non-pyrogenic, low protein binding in-line filter (pore size of 0.2 micrometer to 1.2 micrometer).
- Do not coadminister other drugs through the same intravenous line.
- Flush the intravenous line at end of infusion. When administered in combination with ipilimumab, infuse OPDIVO first followed by ipilimumab on the same day.
- Use separate infusion bags and filters for each infusion.

Phase II Pilot Study Evaluating Strategies to Overcome Resistance at the Time of Progression
for Patients with Non-Small Cell Lung Cancers Harboring Major Oncogenic Drivers
Wake Forest Baptist Comprehensive Cancer Center (CCCFWU)
CCCFWU 62716
ClinicalTrials.gov: NCT02949843

Disposal: Caution should be exercised in handling and preparing OPDIVO for Injection, USP. Several guidelines on this subject have been published. To minimize the risk of dermal exposure, always wear impervious gloves when handling vials containing OPDIVO for Injection, USP. Dispose through the Institutional waste stream and guidelines.

10.0 Correlative Studies

NA

11.0 Data Management

Informed consent document	ORIS
Patient eligibility form (Appendix A)	ORIS
Protocol registration form (Appendix B)	ORIS
Tobacco Use Case Report form: Baseline (Appendix D)	REDCap
Tobacco Use Case Report form: Progression (Appendix E)	REDCap
Adverse Event Log (Appendix F)	ORIS
RECIST Data collection form (Appendix H)	REDCap
Enrollment Mutation Case Report form (Appendix I)	REDCap
Progression Mutation Case Report form (Appendix J)	REDCap
Data Collection Form: Performance Status (Appendix L)	REDCap

12.0 Statistical Considerations

12.1 Introduction

By design patients will be enrolled in this study prior to the determination of their PD-L1 status. In addition, among patients with low PD-L1 expression (<50%) it cannot be determined prospectively how many patients after disease progression will have a secondary oncogenic driver identified. Thus, patients upon enrollment may enter one of three arms to be determined at a later time – 1) PD-L1 expression $\geq 50\%$, 2) PD-L1 expression <50% with secondary oncogenic driver identified and 3) PD-L1 expression <50% without secondary oncogenic driver identified. It is anticipated that less than 50% of patients will have PD-L1 expression $\geq 50\%$, thus this arm – which is the focus of the primary objective – will take longer to fill. In order to manage the overall sample size expectations of this study, the design will allow enrollment to continue until 15 patients are enrolled in the PD-L1 expression $\geq 50\%$ arm (sample size needed based on Simon's two stage design described below). Each of the other two arms will allow enrollment until a minimum of 15 and maximum of 30 patients are enrolled into each arm. If the maximum (n=30) is reached in either of the PD-L1 expression < 50% arms, then new patients eligible for those arms will not be included in the follow-up assessments.

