3.0 Patient Selection

3.1 Inclusion Criteria

- 3.1.1 Patients must have histologically or cytologically confirmed incurable non-small cell lung cancer that harbors an activating mutation in EGFR, MET, BRAF, V600E, RET, HER2, translocation in Alk, or translocation in ROS-1.
- 3.1.2 Patients must be receiving treatment or planning to start treatment with a tyrosine kinase inhibitor targeting the activated gene.
- 3.1.3 Patients may not be receiving the treatment targeting the activated gene as part of a clinical treatment trial other than the Precision Oncology Trial.
- 3.1.4 ECOG performance status of 0-3.
- 3.1.5 Patients must have normal organ function as defined below:
 - AST(SGOT)/ALT(SGPT) $\leq 2.5 \times$ institutional upper limit of normal
- 3.1.6 These agents may be teratogenic; therefore, women of child-bearing potential and men must agree to use adequate contraception (hormonal or barrier method of birth control) prior to study entry and for the duration of study participation. Should a woman become pregnant or suspect she is pregnant while participating in this study, she should inform her treating physician immediately.
- 3.1.7 Ability to understand and the willingness to sign an IRB-approved informed consent document

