6.2 Treatment Administration

Patients currently receiving or about to start treatment with an oral tyrosine kinase inhibitor for one of the major oncogenic drivers (EGFR, MET, BRAF, V600E, RET, HER2, Alk, or ROS-1) will be eligible. At the time of registration, blood samples will be obtained for plasma and other biomarker analyses (Appendix J), tobacco use (Appendix D) and performance status (Appendix K) will be determined. Treatment with an agent targeting the primary oncogenic driver will be continued until progression. If a new agent is approved for treatment of the primary driver, patients may be changed prior to progression at the investigator's discretion.

At the time of progression, patients will undergo repeat biopsy to determine PD-L1 staining and large scale genetic testing. Foundation Medicine testing is preferred but patients may have testing performed by other platforms including Guardant 360. Other platforms may be used after discussion with the principal investigator. Research plasma and tissue will be collected (Appendix J). Patients will also complete a detailed tobacco use questionnaire at the time of progression (Appendix E). Further, Performance Status will be determined (Appendix K). While awaiting results of testing, patients may continue the current treatment targeting the primary oncogenic driver.

Phase II Pilot Study Evaluating Strategies to Overcome Resistance at the Time of Progression
for Patients with Non-Small Cell Lung Cancers Harboring Major Oncogenic Drivers
Wake Forest Baptist Comprehensive Cancer Center (CCCFWU)
CCCFWU 62716
ClinicalTrials.gov: NCT02949843

If the PD-L1 testing result is $\geq 50\%$, patients will receive immunotherapy with either nivolumab or pembrolizumab as subsequent treatment. If patients have PD-L1 testing result that is $< 50\%$, the large scale testing will be used to determine the presence of absence of a secondary driver. For the purposes of the study, a secondary oncogenic driver will be considered an activating genetic change in a gene other than the primary oncogenic driver gene that has an effective treatment. These would include EGFR, Alk, ROS-1, MET, BRAF V600E, RET, and HER2. Classification of a genetic alteration as a secondary driver will be determined by the investigator.

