12.3 Analysis of Secondary Objectives

Overall survival (OS) will be determined from the date of progression on primary targeted treatment to death. The three cohorts of interest, described above, will have OS estimated using Kaplan-Meier methods and survival rates will be compared using log-rank tests. Next, objective response rates will be estimates in the two PD-L1 expression < 50% arms. Confidence intervals for each of these rates will be estimated. An exploratory comparison will be made among the three groups comparing CR/PR vs SD/PD among the groups using a Fisher's exact test (for the 2x3 table).

Toxicities for each group will be estimated and described using counts and frequencies by grade, location and relatedness.

The incidence of mutations in secondary genes will be determined for patients in the two PD-L1 expression < 50% arms as well. Next, we will examine whether smoking status (defined as Current, Former, Never) is related to the prevalence of any mutations identified (present/absent) using Cochran-Maentel Haenzel tests. These tests will be performed overall and then separately in the three arms defined above

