12.4 Power and Sample Size

As described above the primary power calculation for this study is based on the Simon two-stage design to test the null hypothesis that the objective response rate is 10% versus the alternative that it is 40% in the high PD-L1 expressing group. With the design described above there is 90% power with a sample size of 15. Furthermore, in the two other arms (with sample sizes between 15 to 30 total patients each), we can estimate the rate of CR/PR (for objective response rate) with precision of $\pm 18.7\%$ (for n=30) or $\pm 26.1\%$ (for n=15) using 2-sided Exact Clopper-Pearson confidence intervals.

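### If a PD-L1 <50% arm reaches its cap of 30, section 12.1 leaves later progressors out of follow-up, keeps the earliest ones, and conflicts with the survival follow-up rule in 6.5

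*Combined protocol and SAP*

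**What the plan says.** Section 3.1.2 admits patients at any point in targeted treatment: "Patients must be receiving treatment or planning to start treatment with a tyrosine kinase inhibitor targeting the activated gene". Section 12.1 adds that "By design patients will be enrolled in this study prior to the determination of their PD-L1 status". The arm is set later, under section 6.2: "At the time of progression, patients will undergo repeat biopsy to determine PD-L1 staining and large scale genetic testing".

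On size, section 12.1 says "the design will allow enrollment to continue until 15 patients are enrolled in the PD-L1 expression" ≥50% arm. For the two PD-L1 <50% arms, "Each of the other two arms will allow enrollment until a minimum of 15 and maximum of 30 patients are enrolled into each arm". Once either has 30, "then new patients eligible for those arms will not be included in the follow-up assessments". Section 12.4 plans these arms "with sample sizes between 15 to 30 total patients each", and section 12.6 gives a total of 45 to 75.

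In section 12.3, "Overall survival (OS) will be determined from the date of progression on primary targeted treatment to death". The three cohorts are compared by Kaplan-Meier and log-rank, with no adjustment. Response is compared by an exploratory Fisher test. Secondary-mutation incidence is determined in the two PD-L1 <50% arms. Section 5.2.1 makes overall survival (OS) by cohort the first secondary outcome.

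Section 6.5 has survival monitored until death and makes no exception for patients above the cap.

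**The concern.** Nobody can be placed in a PD-L1 <50% arm before progressing, so these arms fill in calendar order of progression. A cap of 30 then keeps the first 30 to progress and excludes those who took longer. An arm that stays below 30 keeps everyone. If time to progression is related to later survival, the cap selects on a prognostic variable in one arm and not in the arm it is compared with.

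Two further consequences need no prognostic assumption. The over-cap patients have consented, registered and come to the progression biopsy, yet their place in the OS analysis is undefined because 12.1 and 6.5 disagree. The incidence of secondary mutations also depends on whether these patients count in the denominator, which 12.3 does not say.

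**Working it through.** **The plan's own figures.** Exact two-stage binomial (stop at 0 of 8; reject at 4 or more of 15) gives type I error 0.0544 at 10% and power 0.9046 at 40%, as section 12.2 states. The largest Clopper-Pearson half-widths are 0.187 (n=30) and 0.261 (n=15), as in 12.4. Totals are 3×15 = 45 and 15+30+30 = 75, as in 12.6. The 75 does not count over-cap patients.

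**Inputs.** From the documents: 20 registrations a year (12.5), arms filled by date of progression (6.2, 12.1), cap 30, minimum 15, and a PD-L1-high share below 50% with no point estimate (12.1). Assumed: exponential time from registration to progression, median 12 months, the same in every arm; shares as stated. Arm 1 is PD-L1-high, Arm 2 is PD-L1-low with a secondary driver, and Arm 3 is PD-L1-low without one.

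**Is the cap reached?** Suppose enrolment stops at the 15th PD-L1-high patient. The number N entering Arm 3 by then is negative binomial with 15 successes and success probability p = share1/(share1+share3).
- At 25/15/60%: p = 0.25/0.85 = 0.294, E(N) = 15×0.60/0.25 = 36, P(N>30) = 0.667, expected excess over 30 = 7.8.
- At 40/30/30%: p = 0.40/0.70 = 0.571, P(N>30) below 0.001.
- With the commoner arm holding 80% of PD-L1-low patients: P = 1.00, 0.90, 0.67, 0.36, 0.04 and 0.001 at 10, 20, 25, 30, 40 and 50% PD-L1-high. With an even split: 0.44 at 20% and 0.03 at 30%.

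If each other arm must also reach its minimum of 15, a rare Arm 2 sets the stop. At 25/15/60%, Arm 3 has about 15×0.60/0.15 = 60 patients when Arm 2 has 15, about 30 over the cap. At 40/12/48% the cap is reached in 97% of simulated trials, against 3% under the first reading. At 40/30/30% it is about 0-1% under either.

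**Simulated results at 25/15/60%:**

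| | Stop at 15th PD-L1-high | Other arms also reach 15 |
|---|---|---|
| Cap reached | about 64% (exact 0.667) | about 99% |
| Patients dropped | about 7 (exact 7.8) | about 30 |
| Mean months to progression, kept | 9.7 | 10.0 |
| Same, dropped | 14.6 | 15.4 |
| Same, Arm 2 | about 11 | 12.7 |
| Incidence, capped vs all | 23% vs 20% | 34% vs 21% |
| Spurious OS hazard ratio, Arm 3 vs Arm 2 | 1.03-1.05 | 1.06-1.10 |

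Months run from registration. The hazard-ratio row assumes post-progression hazard proportional to (months + 0.5) to the power -0.3 to -0.5, which is not in the documents. The incidence row can be approximated by hand: under the second reading 15/(15+30) = 33% capped against 15/(15+60) = 20% with all counted.

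**Sensitivity to the median** (20% PD-L1-high, commoner arm 80% of the rest). Mean months for kept against dropped are 6.2 and 8.3 (median 6), 9.7 and 14.7 (median 12), 12.1 and 19.3 (median 18). The direction does not change.

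**Against the noise.** With 30 and 15 deaths, SE(log HR) = √(1/30 + 1/15) = 0.316, so a 95% interval spans a factor of exp(1.96×0.316) = 1.86 each way. ln(1.03)/0.316 = 0.1 SE and ln(1.10)/0.316 = 0.3 SE. In a separate simulation of Arm 1 against the capped arm, with equal true OS and assumed correlation 0.3 to 0.6 between the two times, nominal 5% rejection was 0.05 to 0.075 with the cap and 0.054 to 0.061 without (10% to 20% PD-L1-high).

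**The case against.** A reader might infer that the commoner arm will over-represent fast progressors and that this materially tilts the OS and response comparison. The documents do not support that.
- The effect exists only if an arm passes 30, and the plan says only that fewer than half will be PD-L1-high.
- The enrolment stop cuts off late progressors in every arm, so only the gap between the cap date and the stop date biases a comparison.
- No link between time to progression and later survival is given.
- The arms are non-randomised and treated differently, and the response comparison is labelled exploratory.

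Large figures can be produced, such as a hazard ratio of 1.21 at 30/10/60%. They require every arm to reach 15, and that scenario needs about 178 registrations over 9 years, against 45 to 75 patients over at least 3 years in section 12.6. Even 25/15/60% under that rule needs about 128 registrations, or 128/20 = 6.4 years.

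A reader might also say that the kept patients had shorter benefit from their targeted drug. Section 3.1.2 admits patients already on treatment, so the order is by time from registration, not total drug time; allowing for prior treatment weakens the bias. Nor are patients' data discarded: 12.1 removes follow-up assessments only, and nothing says biopsy or mutation results are dropped.

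These limits stand. The stated exclusion, its conflict with 6.5, and the undefined incidence denominator remain.

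**Conclusion.** The point holds as a conditional one. If a PD-L1 <50% arm reaches 30, the plan keeps the earliest progressors after registration (about 10 months on average, against about 15 in those dropped, at an assumed median of 12). It also leaves registered patients out of follow-up that 6.5 appears to require. At assumed shares of 25/15/60% the number affected is about 7 or about 30, depending on how the stopping text in 12.1 is read; at 40/30/30% it is essentially none.

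The OS bias is small (hazard ratio roughly 1.03 to 1.10 at 25/15/60%), rests on an assumed prognostic link, and is well inside the imprecision of 15 against 30 patients. The primary single-arm test is untouched. The possible inflation of secondary-mutation incidence rests only on the assumed shares and on how the denominator is read. This is an inexpensive improvement to a secondary analysis, not a threat to the trial's main conclusion.

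**What to change.** Change 12.1 so that reaching 30 ends only protocol-specific follow-up visits, and reconcile it with 6.5. Keep every classified PD-L1 <50% patient in the OS analysis by vital status and in the mutation-incidence denominator of 12.3.

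For response, either keep the first 30 per arm, or include all over-cap patients and count those without a scan as non-responders. Do not add only those who have a scan: section 6.1 leaves imaging outside nivolumab and pembrolizumab to the investigator's discretion, so that would introduce a new selection.

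State in 12.1 whether enrolment stops at the 15th PD-L1-high patient or waits for 15 in each arm, since this largely decides how many patients exceed the cap. Optionally, record the start date of the targeted drug on Appendix I and add a supportive Cox model adjusting for time on that drug. Section 12.3 has no survival model at present, so this would sit beside the log-rank test.

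Cost: wording, one optional date field, and vital-status follow-up of a few to about 30 already registered patients at 25/15/60%, possibly more if secondary drivers are rarer. No extra enrolment.
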